Our long-term objective is to evaluate the efficacy of curcumin (CC) in preventing a recurrence of chronic subdural hematoma (cSDH) following surgical evacuation. Recurrence is defined as an increase in total hematoma volume on the operated side compared to a post-operative day one CT scan with persistent or recurrent neurological symptoms. We propose this pilot study to assess feasibility and obtain preliminary benefit assessment of the proposed therapeutic approach.

Objective 1: To determine if the use of CC treatment reduces the total hematoma cavity volume over a 6-month interval, compared to a post-subdural drain removal CT scan. This evaluation is expected to offer sufficient evidence for a larger definitive trial.

Objective 2: Study the effect of CC on interleukin-8 (IL-8)-induced disruption of endothelial permeability *in vitro* using human vascular endothelial cells.

Central hypothesis: CC treatment prevents the re-accumulation of cSDH, which may occur by inhibition of IL-8 and allowing resolution of the total hematoma cavity volume over six months.

2. Background

Chronic subdural hematomas (cSDH) are extra-axial fluid collections in the cranium that can result in brain compression and neurological decline. cSDH commonly occurs after traumatic brain injury (TBI); though, many times there is no history of trauma. The incidence of cSDH is expected to significantly rise, due to an increasing elderly population worldwide. This is a common and challenging neurosurgical problem due to their ability to recur requiring repeated surgical re-evacuation. Repeat surgery comes with additional morbidity as well as rising costs for both patients and hospitals. The literature reported recurrence rates ranging from 2.3% to 33%.^{8,29,32,40}

We recently completed a retrospective review of 147 chronic unilateral, subdural hematomas and 75 chronic bilateral subdural hematomas at our institution from 2007-2014 (IRB#14-160). The data show that 15.65% of the unilateral group and 9.33% of the bilateral group showed recurrence.¹⁷ Operative decompression is the treatment of choice; however, an effective therapy preventing recurrence of cSDH after surgical intervention has not yet been found. Our long-term goal is to develop a therapeutic approach focused on the prevention of cSDH recurrence after initial surgical intervention.

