cSDH patients will take one capsule three times a day for up to 60 days. Because maximum treatment duration is 60 days, IDS will dispense a total of 180 capsules. IDS will dispense this amount on two occasions to reduce waste and save cost for cases in which treatment may end early. They will undergo standard post-operative care in regard to imaging and clinical follow-up.

- Patients will begin taking placebo or CC within 24 hours post-operatively and able to take oral medication. It will then be continued TID.
- CT Imaging:
 - Pre-operative CT SOC scan
 - If the hematoma volume is < 115 cc, the patient will not be included in the study
 - Post-operative day one CT SOC scan within 24 hours of surgery.
 - Post subdural drain removal SOC scan usually 1-2 days after surgery.

Title: Clinical Action of Curcumin/Turmeric In chronic Subdural hematoma recurrence (CACTIS)

- If the residual total hematoma cavity volume is $<80\text{cc}$, the patient will be dropped from study, as the curcumin has not had time to influence the patient's reabsorption.
- *During the SOC one week follow-up appointment without a CT scan*, the attending will decide on the need for a repeat CT scan in 4 weeks based on the patient's **post-subdural drain removal SOC scan**.
 - If the residual total hematoma cavity volume is $\geq 80\text{cc}$, the patient will receive an additional CT scan (SOC) for an appointment one month following the previous appointment (Approximately post-operative day 37)
 - If there is a decline in neurological exam or other clinical concern, the neurosurgeon may perform an earlier CT scan
- This will continue on a monthly basis for 6 months, or until residual total hematoma cavity volume is $< 80\text{cc}$
 - **Resolution** will be defined as residual total hematoma cavity volume $< 80\text{cc}$
 - Patients with resolution of their hemorrhage will no longer require Tx or follow-up visits. Their pills will be returned and discarded. These patients will receive phone **call** follow-ups at 1-month, 6-month, and 18-month intervals

All radiographic imaging discussed here is our institution's standard of care for the management of SDH. If Tx discontinued, the patients will still be followed according to the schedule below

- Study Follow-Up **Phone Calls**
 - 1 month, 6 months, 18 months
 - Modified Ranking Scale (MRS) (Appendix 3)
 - Markwalder Grading Scale (Appendix 4)

5. Study Endpoints

5.1. Describe the primary and secondary study endpoints.

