- 5.1.1. Primary: Change, rate of change, and time-to-resolution in total hematoma volume of cSDH compared to post-subdural drain scan of less than 80cc in post-surgical patients
- 5.1.2. Secondary: Recurrence rate of cSDH
- 5.1.3. Secondary: Markwalder and mRS progression.
- 5.1.4. Secondary: Rate of surgical intervention in CC and placebo groups.
- 5.1.5. Secondary: Rate of persistent or recurrent neurological symptoms in CC and placebo groups.

5.2. Safety Endpoints:

- 5.2.1. To assess the tolerability of CC in patients via frequency of any side effects, or adverse events as defined by the National Institute of Health's Common Terminology Criteria for Adverse Events (NCI-CTCAE, Version 4.0)
- 5.2.2. Subject participation will be terminated if any reported adverse events, discomfort, or distress is detected.

6. Research Setting

This is a single center study that will take place at the University of New Mexico Hospital. New patients admitted directly to the UNM Neurosciences Intensive Care Unit (NSICU) as a transfer from

Title: Clinical Action of Curcumin/Turmeric In chronic Subdural hematoma recurrence (CACTIS)

an outside hospital as well as patients admitted directly through the UNM Emergency Department (ED), with subdural hematomas will be identified and recruited as potential subjects. All surgical operations will take place in the main operating room (OR) at UNMH. The perioperative care of the enrolled patients, as well as the non-surgically managed patients will take place both in the NSICU as well as the Neurosurgical step-down unit.

Once patients have been discharged from the hospital, all follow-up appointments will take place in the Clinical Neurosciences Center located adjacent to UNMH. Patients will follow-up in the subdural clinic, staffed by **[name]**, Principal Investigator.

7. Resources Available

[name] is the chairman of the Department of Neurosurgery. He has been a part of the UNM faculty since 2005, and has significant experience with both the surgical/medical management of patients with subdural hematomas, as well as with oversight on research projects. [name] is personally responsible for the development of the 24-bed Neurosciences ICU where neurosurgical patients are cared for, as well as the multidisciplinary Neurosciences center where patients are followed in an outpatient setting. **He will see all patients enrolled in the trial in his clinic.**

[name] has participated in two clinical trials.

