 - c. For the next patient, we will first determine the hematoma cavity volume group; this patient's Tx assignment (CC or placebo) will be alternate to the immediately preceding patient. This process is repeated until all of the patients are enrolled.
3. The patients will start medication **within 24 hours after surgery**, or as soon as they are able to take oral medication
 - a. 1 capsule three times a day (with breakfast, lunch, and dinner) for a maximum of 60 days or until resolution of subdural hematoma
 - b. Resolution will be defined as residual total hematoma cavity volume $<$ 80cc
 - i. If the post-subdural drain removal scan demonstrates a residual total hematoma volume $<$ 80cc, the patient will not be included in the study sample; although, the patient may receive more than one dose of CC by the time of the CT scan.

- CT Imaging:
 - Pre-operative CT SOC scan-- If the hematoma volume is $<$ 115 cc, the patient will not be included in the study
 - Post-operative day one CT SOC scan
 - Post subdural drain removal SOC scan--If the residual total hematoma cavity volume is $<$ 80cc, the patient will be removed from study, as the curcumin has not had time to influence the patient's reabsorption.
 - During the SOC 1 week follow-up appointment, the attending will decide on the need for a repeat CT scan in 4 weeks based on the patient's **post-subdural drain removal SOC scan**. The considerations for re-evacuation include: lack of resolution of the initial clot, an obvious increase in size of the clot, persistent headache, onset of seizures, or onset of new deficit or headache. These criteria will be used in all subsequent considerations for surgical re-evacuation.

Title: Clinical Action of Curcumin/Turmeric In chronic Subdural hematoma recurrence (CACTIS)

- If the residual total hematoma volume is $\geq 80\text{cc}$, the patient will receive an additional CT scan (SOC) for an appointment one month following the previous appointment (Approximately post-operative day 37)
- If there is a decline in neurological exam or other clinical concern, the neurosurgeon may perform an earlier CT scan
- This will continue on a monthly basis for 6 months, or until residual total hematoma cavity volume is $< 80\text{cc}$
 - **Resolution** will be defined as residual total hematoma cavity volume $< 80\text{cc}$
 - Patients with resolution of their hemorrhage will no longer require follow-up visits. Their pills will be returned and discarded.

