- a. For patients with a residual total hematoma cavity volume $\geq 80\text{cc}$, the neurosurgery attending will determine if the patient requires surgical re-evacuation for a 1 month follow-up in clinic with a repeat Head CT. The considerations for re-evacuation include: lack of resolution of the initial clot, an obvious increase in size of the clot, persistent headache, onset of seizures, or onset of new deficit or headache. These criteria will be used in all subsequent considerations for surgical re-evacuation.
- ii. If there is a decline in neurological exam or other clinical concern, the neurosurgeon may perform an earlier CT scan. The patient will continue to take the placebo or CC three times a day.
3. Patients presenting for their 2nd clinic appointment (Approximately post-operative day #37):
 - a. Repeat CT scan will be performed on the day or near the day of the appointment
 - b. Subdural thickness measurements of remaining subdural fluid will be completed
 - i. Patients with a residual total hematoma cavity volume $< 80\text{cc}$ will be instructed to discontinue the pills. Unused medication will be retrieved from the patients and returned to IDS for destruction. They will not have additional neurosurgical imaging or follow-up required, unless deemed necessary by the neurosurgery attending.
 1. They will continue to be followed by the study team with a 6 month and 18-month phone call
 - ii. For patients with a residual total hematoma cavity volume $\geq 80\text{cc}$, the neurosurgery attending will determine if the patient requires surgical re-evacuation as previously described for a 1 month follow-up in clinic with a repeat Head CT. If there is a decline in neurological exam or other clinical concern, the neurosurgeon may perform an earlier CT scan. The patient will continue to take the placebo or CC three times a day.
 4. Patients presenting for their 3rd clinic appointment (Approximately post-operative day #67):
 - a. Repeat CT scan will be performed on the day or near the day of the appointment
 - b. Subdural thickness measurements of remaining subdural fluid will be completed
 - i. Patients with a residual total hematoma cavity volume $< 80\text{cc}$ will be instructed to discontinue the pills. Unused medication will be retrieved from the patients and returned to IDS for destruction. They will not have additional neurosurgical imaging or follow-up required, unless deemed necessary by the neurosurgery attending.

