 1. They will continue to be followed by the study team with a 6 month and 18-month phone call
 - For patients with a residual total hematoma cavity volume $\geq 80\text{cc}$, the neurosurgery attending will determine if the patient requires surgical re-evacuation as previously described for a 1 month follow-up in clinic with a repeat Head CT. If there is a decline in neurological exam or other clinical concern, the neurosurgeon may perform an earlier CT scan.
 5. Patients will not take CC pills or placebo longer than 60 days. If there are extra pills, they will be properly retrieved and returned to IDS for destruction.

All radiographic imaging discussed here is our institution's standard of care for the management of SDH. If a patient is discontinued, they will still be followed by the research team until the end of the trial (see below).

Follow-up outcome assessments (Modified Ranking Scale (MRS); Markwalder Grading Scale, [MGS]) will be obtained 1 month, 6 months, and 18 months following surgery for research. All data are coded

Title: Clinical Action of Curcumin/Turmeric In chronic Subdural hematoma recurrence (CACTIS)

with a unique identifying number to maintain confidentiality. This exam assesses the patient's neurological status to predict additional progress and evaluate functional status. This exam will be conducted with the use of a structured interview (see attached MRS questionnaire) by phone or in person if the patient has a scheduled appointment by one of the researchers.

[figure not shown]
- Study Follow-Up Phone Calls
 - 1 month, 6 months, 18 months
 - Modified Rankin Scale (MRS)
 - Markwalder Grading Scale

Modified Rankin Scale (mRS)

Score	Degree of Disability
0	No symptoms
1	No significant disability. Able to carry out all usual activities, despite some symptoms
2	Slight disability. Able to look after own affairs without assistance, but unable to carry out all previous activities.
3	Moderate disability. Requires some help, but able to walk unassisted.
4	Moderate severe disability. Unable to attend to own bodily needs without assistance, and unable to walk unassisted.
5	Severe disability. Requires constant nursing care and attention, bedridden, incontinent.
6	Dead.

Markwalder Grading Scale

Mental Status	Neurologic Findings	Grade
normal	Normal	0
fully alert and conscious; may have mild symptoms such as headache	none or mild (reflex asymmetry – i.e. Pronator Drift)	1

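### Scheduled visits and CT stop at resolution, so crude rates of recurrence, re-operation and symptoms may be biased towards the arm that resolves faster

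*Combined protocol and SAP*

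**What the plan says.** Section 5 lists three secondary endpoints that are event rates: recurrence, surgical intervention, and the symptom endpoint ("Secondary: Rate of persistent or recurrent neurological symptoms in CC and placebo groups"). The objectives say "Recurrence is defined as an increase in total hematoma volume on the operated side compared to a post-operative day one CT scan", accompanied by neurological symptoms, so a later CT is needed before a recurrence can be counted.

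Follow-up then splits by cavity volume.

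- **At or above 80cc.** Section 9, Study Procedures, sets visits with CT at about days 37 and 67 and adds: "This will continue on a monthly basis for 6 months, or until residual total hematoma cavity volume is" below 80cc. Re-evacuation is considered at these visits.
- **Below 80cc.** The Study Timelines state "Patients with resolution of their hemorrhage will no longer require Tx or follow-up visits". On imaging, the Clinic Follow-up text states "They will not have additional neurosurgical imaging or follow-up required, unless deemed necessary by the neurosurgery attending". What remains on the schedule is phone contact: "They will continue to be followed by the study team with a 6 month and 18-month phone call". The Study Timelines also list a 1-month call.

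The listed content of the calls is mRS and Markwalder. For all patients these scores "will be obtained 1 month, 6 months, and 18 months following surgery for research".

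The Statistical analysis text compares re-operation and recurrence with Fisher's exact test and logistic regression, and also compares rates of symptom removal and new symptoms. It says nothing about unequal surveillance.

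**The concern.** Resolution happens after randomisation and is part of the primary endpoint. If curcumin shortens the time to 80cc, curcumin patients leave the monthly visit-and-CT schedule sooner, and any later event in them has fewer scheduled chances to be found. The counted rates can then differ between arms even when the true rates do not. Blinding does not prevent this, because follow-up responds to the measured volume and not to the assignment.

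The pilot is meant to supply effect sizes and to try out a working definition of recurrence for a larger trial. At stake is an estimate, and a recurrence measure, that partly reflects how long each arm was watched.

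**Working it through.** The plan gives no figure for ascertainment, so there is none to reproduce.

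**1. Scheduled contacts after day 37.** A patient who stays unresolved has visits with CT at about days 67, 97, 127, 157 and 187, that is five. A patient resolved at day 37 has one call up to month 6 if calls are counted from surgery, because the 1-month call has already passed. If the call intervals start at resolution, there are two.

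**2. What the calls can show.** mRS 0 means no symptoms and Markwalder 1 mentions headache, so a symptom still present at the call should register. A symptom that came and went, a CT, or an operation since the last contact is not among the listed items.

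**3. Size under stated assumptions.** Inputs:

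- True event rate R = 15.65% in both arms (the centre's unilateral series, Background). Sensitivity values are 9.33% (its bilateral series) and 33% (top of the literature range).
- 24 patients per arm (section 4). The Statistical analysis text says 25, which barely changes the result.
- Assumed: constant event hazard to day 187, and exponential time to resolution, recognised at CTs on days 37, 67, 97, 127, 157 and 187.
- Assumed: full detection before recognised resolution and detection d afterwards. Resolution by day 187 (placebo/curcumin) is 40/60%, 50/75%, 60/90% or 25/75%.

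Counted rate = R × [1 − s × (1 − d)], where s is the share of events falling after recognised resolution. For cumulative resolution p, the proportion recognised by scan day c is 1 − (1 − p)^(c/187). Weighting by the share of events in each interval after that scan (0.166, 0.162, 0.158, 0.153, 0.149; the other 0.212 fall before day 37, when nobody has yet left the schedule):

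- p = 50%: 0.128×0.166 + 0.220×0.162 + 0.302×0.158 + 0.375×0.153 + 0.441×0.149 = 0.228
- p = 75%: 0.240×0.166 + 0.391×0.162 + 0.513×0.158 + 0.610×0.153 + 0.688×0.149 = 0.380

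At d = 0, placebo is 15.65% × (1 − 0.228) = 12.1% and curcumin is 15.65% × (1 − 0.380) = 9.7%. The other cases follow in the same way:

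| Resolution, placebo/curcumin | d | Counted, placebo vs curcumin | Difference (points) | Ratio | Patients per 24 |
|---|---|---|---|---|---|
| 40/60% | 0.75 | 15.0% vs 14.5% | 0.4 | 0.97 | 0.1 |
| 50/75% | 0.5 | 13.9% vs 12.7% | 1.2 | 0.91 | 0.3 |
| 50/75% | 0 | 12.1% vs 9.7% | 2.4 | 0.80 | 0.6 |
| 60/90% | 0 | 11.2% vs 7.7% | 3.6 | 0.68 | 0.9 |
| 25/75% | 0 | 14.0% vs 9.7% | 4.3 | 0.69 | 1.0 |
| any | 1 | 15.65% vs 15.65% | 0 | 1.00 | 0 |

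Over the same grid the difference is 0.25 to 2.6 points at R = 9.33% and 0.85 to 8.7 points at R = 33% (8.7% × 24 = about 2 patients).

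**4. If risk after resolution is low.** The cited imaging study found 97.4% without recurrence when the post-drain cavity was below 80cc, a risk of 2.6%. The difference in missed events is (difference in resolution) × 2.6% × (1 − d). It runs from 0.20 × 2.6% × 0.5 = 0.26 points to 0.50 × 2.6% × 1 = 1.3 points, or 0.06 to 0.31 patients per 24. That group is removed from this trial, so the figure is only a guide for patients who cross 80cc later.

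**The case against.** Several parts of the plan limit the problem, and they stand.

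- The Background (CT Scans) says a neurological change prompts an earlier CT whatever the volume, and the attending may order imaging after resolution. Recurrence requires symptoms, so detection after resolution is probably above zero. This still depends on the team hearing of the symptoms between calls.
- Reasons for re-evacuation are recorded and fluid is collected at recurrence surgery, so re-operations at this hospital should be known without a call.
- A clot that fails to resolve is itself a consideration for re-operating. Fewer re-operations after faster resolution may be genuine benefit, and the documents cannot separate that from fewer occasions to detect or decide.
- The mRS and Markwalder scores are scheduled alike for everyone and are not affected in this way.
- The call interview refers to an attached questionnaire that is not in the text available, so its content may be wider than the two scales listed.

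A reader might go further and infer a false reduction of 14% or 33%. With 50% of curcumin and 25% of placebo patients resolved at day 37, 15.65% × (0.5 + 0.5 × 0.5) = 11.7% against 15.65% × (0.75 + 0.25 × 0.5) = 13.7%; with no detection by calls, 7.8% against 11.7%. The documents do not support this as the expected size. It applies lost detection to every event, including those before day 37, gives resolved patients full risk, and in the second case ignores symptom-triggered CT. Nor does the text show that patients are likely to re-present elsewhere: it says only that outside hospitals transfer patients to this centre.

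**Conclusion.** The asymmetry is in the text, and its direction is clear: whenever detection after resolution is incomplete and one arm resolves faster, the crude rates favour that arm. The size cannot be determined from the documents. At a true rate of 15.65% and under the assumptions above it is about 0.4 to 4.3 points, at most about one patient per 24. It would be smaller if risk after resolution is low or symptom-triggered CT works well, and larger only if events are much commoner. The imaging difference ends at month 6, after which nobody has scheduled CT.

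This does not show that a lower event rate in the curcumin arm would be an artefact, nor does it threaten a significance test in a trial this small. It weakens the secondary effect estimates and the recurrence measure that the pilot is to hand on. The change is worth making before follow-up starts, because interval events that nobody asked about are hard to reconstruct.

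**What to change.** Anchor event ascertainment to the 1-, 6- and 18-month assessments already planned for every patient, whatever the volume.

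- At each one, ask the same fixed questions about the whole interval since the previous one of these assessments: new, returned or persisting neurological symptoms; any head CT; any subdural surgery at any hospital; with dates. Asking at every clinic visit instead would still question unresolved patients more often.
- At month 6, check this hospital's records for every patient. Request outside scans and operation notes when an answer is yes.
- Compare re-operation and symptom rates to 6 months on this common ascertainment.
- Recurrence needs a CT, which questions cannot replace. Report recurrences found on symptom-triggered imaging separately from those found only on scheduled monthly CT, add a sensitivity analysis limited to the symptom-triggered ones, and state that scheduled imaging differs by resolution status.
- Reconcile the call schedule after resolution (6 and 18 months in one place, 1, 6 and 18 in others) and say whether it runs from surgery or from resolution.

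The cost is a short question set on contacts already planned, one record check per patient and occasional record requests. The downside is reliance on patient or proxy recall. No imaging is added.
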